4.6. Safety Analyses

Safety measures include treatment exposure, adverse event (AE), vital signs, weight, hypoglycemia, laboratory measures and immunogenicity. All safety analyses will be based on the SS. Unless otherwise specified, safety analysis period will include both treatment period and follow-up period.

Percentages will be calculated using the SS as the denominator. For events that are genderspecific, the denominator and computation of the percentage will include only participants from the given sex. Unless otherwise noted, Fisher's exact test will be used for treatment comparison and risk difference and 95% confidence intervals will be provided.

For continuous safety variables (for example, laboratory measures, vital signs, and weight), descriptive statistics for the observed values and change from baseline at scheduled visits during the treatment period and follow-up will be provided. For some selected laboratory measures (i.e., liver enzyme tests, lipid measures), the log-transformed values of observed values, change from baseline and percentage change from baseline will be analyzed by the MMRM model using treatment, visit, and treatment by visit as fixed effect, baseline of the dependent variable as a covariate, and compound symmetry as the variance-covariance structure.

The incidence and event rate of participant-reported and CGM-based hypoglycemia will be summarized by treatment and analysis period for different types of hypoglycemia. Analysis details are provided in Section 4.6.3.1.

4.6.1. Extent of Exposure

Duration of exposure to study treatment will be summarized. No p-values will be reported in these tables as they are intended to describe the study populations, rather than test hypotheses about them.

Total patient-years of exposure will be reported. The number and proportion of participants falling into the following different exposure categories will also be summarized by study treatment:

- $>0, \ge 30$ days, ≥ 90 days, ≥ 180 days, ≥ 365 days, ≥ 545 days, and
- >0 and < 30 days, ≥30 and < 90 days, ≥90 and <180 days, ≥180 and < 365 days, ≥365 and <545 days, ≥545 days.

Exposure on study treatment will be calculated as:

- LY3209590: date of the last treatment administration date of first treatment administration + 7 days, and
- Insulin degludec: date of the last treatment administration date of first treatment administration + 1 day.

Total patient-years of exposure will be calculated by the sum of duration of exposure in days divided by 365.25. The following summary statistics will be provided: n, mean, standard deviation, median, minimum, maximum, interquartile range, and total exposure (that is, total patient-years).

All participants who complete the study treatment period are required to complete a safety follow-up period and participants who discontinue the study treatment prematurely are encouraged to remain in the study for safety monitoring. The duration on study from the first dose of study treatment to the study disposition (defined as treatment period disposition or follow up disposition, whichever is later)date will also be summarized by treatment.

A listing of exposure to study treatment and time in study since first dose will be provided.

4.6.2. Adverse Events

Events that are newly reported after the first dose of investigational product (IP) or reported to worsen in severity from baseline will be considered treatment emergent adverse events (TEAEs). The Medical Dictionary for Regulatory Activities (MedDRA) lowest level term (LLT) will be used in the treatment-emergent assessment. The maximum severity for each LLT during the baseline period (see the table in Section 4.1) will be used as baseline severity.

The table below describes the analysis related to AEs.

Analysis	Details		
Overview of AEs	Number and percentage of participants who experienced:		
	• SAE		
	• Death		
	• Discontinuation from study treatment due to an AE		
	Discontinuation from study due to an AE		
	• TEAE		
	• TEAE related to study treatment		

Analysis	Details		
Summary by PT within SOC	Number and percentage of participants with TEAEs using MedDRA PT nested		
	within SOC:		
	• TEAE		
	TEAEs by Maximum Severity		
	• SAE		
	• AE leading to permanent discontinuation of study treatment		
	Events will be ordered by decreasing risk difference within SOC. SOCs will be		
	listed by decreasing risk difference.		
	For each participant and TEAE, the maximum severity for the MedDRA PT is the maximum postbaseline severity observed from all associated LLTs mapping to the MedDRA PT. The maximum severity will be determined based on the non-missing severities.		
Summary by PT (within	Number and percentage of participants with TEAEs using MedDRA PT		
SMQ when applicable)	(irrespective of SOC):		
	• TEAE		
	• Common TEAEs (i.e., occurred in ≥1% before rounding in LY3209590		
	group)		
	• TEAE of safety topic of interest by PT (within SMQ when applicable)		
	Events will be ordered by decreasing risk difference. Whenever applicable SMQs will be ordered by decreasing risk difference.		
Listing	Separate listings for the following events will be provided:		
	• SAE, including death		
	AEs leading to study treatment discontinuation		
	Severe hypoglycemia		
	• Events sent to the external adjudicator for MACE adjudication with		
	adjudicators' assessment		
	• Participants who receive rescue therapy due to severe/persistent		
	hyperglycemia		
	Persistent-recurrent hypoglycemia reported by investigators		
	Persistent-recurrent hypoglycemia identified by programing		
	Medication errors of interest		

Abbreviation: AE = adverse event; LLT = lowest level term; MACE = major adverse cardiovascular event; MedDRA = Medical Dictionary for Regulatory Activities; SAE = serious adverse event; SOC = System Organ Class; PT = preferred term; TEAE = treatment emergent adverse event.

4.6.2.1. Safety topic of Interest

4.6.2.1.1. Severe Hypoglycemia

Severe hypoglycemia is a severe event characterized by altered mental and/or physical status requiring assistance for treatment of hypoglycemia. The determination of a hypoglycemic event as an episode of severe hypoglycemia is made by the investigator based on the medical need of the participant to have required assistance and is not predicated on the report of a participant simply having received assistance. If a hypoglycemic event meets the criteria of severe hypoglycemia, the investigator must record the event as serious on the AE case report form (CRF).

A summary of severe hypoglycemia by PT in decreasing order of risk difference (LY3209590 – insulin Degludec) will be provided. The incidence and event rate during the treatment period will be analyzed using the method described in Section 4.6.3.1. A listing of severe hypoglycemia events will also be provided.

4.6.2.1.2. Persistent-Recurrent Hypoglycemia

The potential risk of persistent-recurrent hypoglycemia (P-R hypoglycemia) will be assessed from the first dose date up to the end of the study. P-R hypoglycemia events will be identified using

- 1. using investigator assessment and clinical judgment to determine if recent repeated hypoglycemia may have contributed to a participant reported hypoglycemic event that degenerated with poor outcomes, and
- 2. using prespecified criteria and timeframe to derive events from e-diary database (see definition in Appendix 10 [Section 6.10]).

Identification of P-R hypoglycemia based on investigator reporting is precipitated by a hypoglycemic event that results in a participant response to questions that are indicative of potential severe hypoglycemia. This information will trigger an e-mail alert notifying the investigator to contact the study participant, obtain more information about the specific hypoglycemic event, and provide them clinical guidance, if appropriate. Hypoglycemic events that trigger alerts to investigators are those participants report in the e-Diary have required treatment with glucagon or IV glucose, resulted in coma, motor vehicle accident or other trauma, hospitalization, inability to treat themselves, or emergency medical care.

Upon receiving the e-mail notification, investigator will access the e-Diary database and answer the following question: "In your clinical judgement, is this hypoglycemia event associated with repeated hypoglycemia events?" Investigator should select "Yes" or "No" as an answer.

During protocol training, investigators are trained to consult the e-Diary database and review participant's blood glucose values and hypoglycemia reports to determine the best answer. If investigator judges the hypoglycemic event that triggered an alert is related to repeated episodes of hypoglycemia, the participant will be identified as having presented a P-R hypoglycemic event reported by the investigator.

P-R hypoglycemia events and participants who present P-R hypoglycemia will be identified by one or both approaches explained above. Summary statistics and a listing of the events identified by both methods will be provided.

4.6.2.1.3. Systemic Hypersensitivity Reactions

Hypersensitivity reactions are exaggerated or inappropriate immunologic responses occurring in response to an antigen or allergen. These can be systemic or localized. At all visits, participants will be evaluated by the investigator for signs and symptoms suggestive of hypersensitivity. Investigators will complete an CRF designed to record additional information about AEs suggestive of a hypersensitivity reaction. The TEAEs of hypersensitivity reactions were identified using MedDRA search of:

- Anaphylactic reaction SMQ (20000021; narrow terms),
- Hypersensitivity SMQ (20000214; narrow terms), and
- Angioedema SMQ (20000024; narrow terms).

The number and percentage of participants who reported a TEAE for the following will be analyzed:

- Any narrow term from any 1 of the 3 SMQs indicated above (that is, combined search across narrow portions of all 3 SMQs), and
- Any narrow term within each SMQ, separately (that is, narrow SMQ search).

Individual PTs that satisfied the query will appear in the summary nested within each SMQ in decreasing order of risk difference (LY3209590 – insulin Degludec).

The analyses above are the starting point for medical interpretation of any apparent differences between treatment groups. For notable events, case review will be applied to make the final determination of whether an event is most accurately described as a potential hypersensitivity reaction to study treatment, or another event that is not clearly associated with study treatment administration. This judgment will be on the basis of totality of information available, including the content of a follow-up CRF collected for potential hypersensitivity events.

4.6.2.1.4. Injection Site Reactions

Injection site reactions (ISR) are AEs localized to the immediate site of the administration of a medication. The evaluation of ISRs will be through the unsolicited reporting of ISR TEAEs and through the use of an Injection Site Reaction Follow-up Form completed by the investigator for each incidence of ISR.

A summary of the number of participants with reported events meeting any of the following categories will be provided:

- MedDRA HLT of Injection site reactions,
- MedDRA HLT of Administration site reactions NEC,
- Lipodystrophies and localized amyloidosis, as represented by PTs of:
 - o lipoatrophy,
 - lipodystrophy acquired,
 - o partial lipodystrophy,
 - o lipohypertrophy,
 - \circ sclerema, and
 - o cutaneous amyloidosis.

The summary will present the number of participants who reported:

- at least one AE meeting any of the above categories,
- any AE in each category, and
- any AE for each PT within a specific category.

The PTs will be listed for summary within each category in decreasing order of risk difference (LY3209590 – insulin Degludec).

The additional data collected on the ISR follow-up forms will be summarized in 2 distinct ways:

- 1. at the participant-level (each participant contributes to totals at most once, regardless of the number of ISR events the participant experienced), and
- 2. at the event level (each separate event contributes to totals, regardless of whether the participant experienced multiple ISR events).

4.6.2.1.5. Neoplasms

The TEAEs of neoplasms will be identified by MedDRA narrow search for the following SMQ:

- Malignant tumours SMQ (20000194, narrow terms), and
- Tumours of unspecified malignancy SMQ (20000195, narrow terms).

A summary will present:

- Any narrow term from any 1 of the 2 SMQs indicated above (that is, combined search across narrow portions of both SMQs), and
- Any narrow term within each SMQ, separately (that is, narrow SMQ search).

The PTs will be listed for summary within each SMQ in decreasing order of risk difference (LY3209590 – insulin Degludec).

4.6.2.1.6. Diabetic Ketoacidosis (DKA)

The DKA will be searched by MedDRA PTs from all TEAEs. The number and percentage of participants experiencing treatment-emergent DKA will be summarized by PT in decreasing order of risk difference (LY3209590 – insulin Degludec).

The following PTs will be used in search of DKA:

- diabetic ketoacidosis,
- ketoacidosis,
- euglycaemic diabetic ketoacidosis,
- ketonuria,
- diabetic ketosis,
- diabetic ketoacidotic hyperglycaemic coma,
- ketosis,
- urine ketone body present,
- blood ketone body,
- blood ketone body increased,
- urine ketone body,
- blood ketone body present, and
- lactic acidosis.

4.6.2.1.7. Diabetic Retinopathy or Maculopathy

The diabetic retinopathy or maculopathy will be searched by MedDRA PTs from all TEAEs. The list of PTs for the search is provided in Appendix 7 (Section 6.7). A summary of treatment-emergent retinopathy or maculopathy by PT in decreasing order of risk difference (LY3209590 – insulin Degludec) will be provided.

4.6.2.1.8. Peripheral Edema

The peripheral edema will be searched by MedDRA PTs (see Section 6.8) from all TEAEs. The number and percentage of participants experiencing treatment-emergent peripheral edema will be summarized by PT in decreasing order of risk difference (LY3209590 – insulin Degludec)..

4.6.2.1.9. Hypokalemia

The TEAEs of hypokalemia will be identified by narrow terms in Hypokalaemia SMQ (20000233). A summary of the number of participants with reported treatment-emergent events meeting the SMQ narrow search criteria by PT in decreasing order of risk difference (LY3209590 – insulin Degludec) will be provided.

4.6.2.1.10. Hyperglycemia

The study treatments were designed as the treatment of hyperglycemia for diabetes patients. Therefore, the hyperglycemia is usually not reported as an AE in diabetes studies. However, if a participant develops severe, persistent hyperglycemia after randomization, a rescue therapy will be considered. A listing of participants who receive rescue medication will be provided.

4.6.2.1.11. Major Adverse Cardiovascular Events (MACE)

Potential cerebrocardiovascular events will be identified by the investigative site or by a medical review conducted by the sponsor or designee. A blinded external Clinical Event Committee will adjudicate the events in a consistent and unbiased manner. Events include:

- death
- Cardiac ischemic events (including *myocardial infarction* or *hospitalization for unstable angina*)
- cerebrovascular events (including *stroke* or *Transient Ischemic Attack [TIA]*)
- hospitalization for heart failure, and
- coronary revascularization procedure

Only confirmed MACE by the adjudication committee will be considered as Safety Topic of Interest. A listing of MACE events reported by investigator, including reported term and adjudication results, will be provided.

4.6.2.1.12. Medication Error of Interest

Medication Errors of Interest (MEI) are defined as medication error adverse events (SMQ 20000224 - narrow and broad terms) that meet the criteria of important protocol deviations (IPD), according to the Trial Issue Management Plan (TIMP) and are indicative of multiple doses. These events are considered important protocol deviations because of their potential to impact participant's safety. For this same reason, these events are considered of special interest among all medication error AEs reported in the trial.

MEIs are categorized as IPDs of 'Investigational Medicinal Product and/or Investigational Device'. Screening and identification of MEIs will occur during routine review of trial protocol deviations and trial level safety reviews.

The number and percentage of participants reported with MEI will be analyzed.

A listing of MEI will also be provided. This listing will indicate if severe hypoglycemia or P-R hypoglycemia occurred after the MEI.

4.6.3. Additional Safety Assessments

4.6.3.1. Hypoglycemic Events

4.6.3.1.1. Participant-Reported Hypoglycemic Events

The following types of hypoglycemia events will be derived in the analysis data sets: documented hypoglycemia as Level 1, Level 2, and Level 3 (severe hypoglycemia) according to definitions based on the American Diabetes Association criteria where:

- Level 1: glucose <70 mg/dL (3.9 mmol/L) and $\ge 54 \text{ mg/dL}$ (3.0 mmol/L);
- Level 2: glucose < 54 mg/dL (3.0 mmol/L);
- Level 3: severe hypoglycemia (confirmed by the investigator to be an event that required assistance for treatment).

A set of Level 1 and Level 2 hypoglycemia events will be identified based on blood glucose reading values reported in the participant e-diary. A Level 3 hypoglycemia event is only confirmed by investigator and may not have an associated blood glucose reading.

If a hypoglycemic event is within 60 minutes of another hypoglycemic event, it is considered as a continuation of the previous event. If there are multiple events within 60 minutes of each other then all such events will be combined into a single episode with

- earliest date time and
- minimum glucose value, if applicable
- maximum severity (Level 1, 2 or 3)
- combining all symptoms and outcomes of the multiple hypoglycemic events.

The combined event starts from the first record with Level 1, 2 or 3, and ends when there are no more events for at least 60 minutes.

Further, all episodes will be classified as nocturnal (occurs between midnight and 0600) or nonnocturnal (occurs between 0600 and midnight) hypoglycemia by the time of the originating event.

The Level 2 and Level 3 events are considered as clinically significant hypoglycemia. Therefore, the analysis on a composite of Level 2 and Level 3 (denoted as Level 2/3) hypoglycemia will also be conducted.

The evaluation of potential persistent/recurrent hypoglycemia events will be through assessment of the clinically significant events confirmed by investigators based on clinical judgment and through events identified by pre-specified criteria (see Section 4.6.2.1.2 and Appendix 9 [Section 6.9] for details) using information based on the participant-reported hypoglycemia.

The details of planed analyses are provided in the table below.

Endpoint	Analysis Period	Statistical Method ^a
Event rate of Level 1	Baseline, 0-6, 0-12, 0-26, 0-52,	Negative binomial regression with treatment,
hypoglycemia events	0-78, 12-26, 26-52, 26-78, 52-	baseline HbA1c and baseline Level 1
(events/participant/year):	78 weeks, post-treatment period	hypoglycemia rate as covariates, log
All documented		(exposure/365.25 days) as the offset in the
		model.
Event rate of Level 2	Baseline, 0-6, 0-12, 0-26, 0-52,	Negative binomial regression with treatment,
hypoglycemia events	0-78, 12-26, 26-52, 26-78, 52-	baseline HbA1c and baseline Level 2
(events/participant/year):	78 weeks, post-treatment period	hypoglycemia rate as covariates, log
All documented		(exposure/365.25 days) as the offset in the
		model.
Event rate of Level 3	Baseline, 0-26, 0-52, 0-78, 26-	Negative binomial regression with treatment
hypoglycemia events	52, 26-78, 52-78 weeks, post-	and baseline HbA1c and baseline Level 3
(events/participant/100	treatment period	hypoglycemia rate as covariates, log
year):		(exposure/365.25 days) as the offset in the
All documented		model.
		If the number of events is too small to run the
		negative binomial regression, exposure
		adjusted rate calculated by total number of
		events divided by total exposure for individual
		patients will be provided and the empirical
		method (see Appendix 9 [Section 6.9] for
E (10/2		details) will be used for treatment comparison.
Event rate of Level 2/3	Baseline, 0-6, 0-12, 0-26, 0-52,	Negative binomial regression with treatment,
hypoglycemia events	0-78, 12-26, 26-52, 26-78, 52-	baseline HbA1c and baseline hypoglycemia
(events/participant/year):	78 weeks, post-treatment period	rate of the same hypoglycemia type as
All documented		offect in the model
Nocturnal		onset in the model.
• Non-nocturnal		The plots of the mean cumulative functions
		(MCFs) by each treatment arm will also be
		created The population mean for cumulative
		number of events up to time t $M(t)$ will be
		estimated using a nonparametric estimation
		method described by Nelson (2003).
Incidence of Level 1	Baseline, 0-6, 0-12, 0-26, 0-52,	Logistic regression with treatment, baseline
hypoglycemia events:	0-78, 12-26, 26-52, 26-78, 52-	HbA1c and baseline Level 1 hypoglycemia
All documented	78 weeks, post-treatment period	incidence as covariates.
Incidence of Level 2	Baseline, 0-6, 0-12, 0-26, 0-52,	Logistic regression with treatment, baseline
hypoglycemia events:	0-78, 12-26, 26-52, 26-78, 52-	HbA1c and baseline Level 2 hypoglycemia
All documented	78 weeks, post-treatment period	incidence as covariates.
Incidence of Level 3	Baseline, 0-26, 0-52, 0-78, 26-	Logistic regression with treatment and baseline
hypoglycemia events:	52, 26-78, 52-78 weeks, post-	HbA1c as covariates.
All documented	treatment period	

Endpoint	Analysis Period	Statistical Method ^a
Incidence of Level 2/3	Baseline, 0-6, 0-12, 0-26, 0-52,	Logistic regression with treatment, baseline
hypoglycemia events:	0-78, 12-26, 26-52, 26-78, 52-	HbA1c and baseline hypoglycemia incidence
All documented	78 weeks, post-treatment period	of the same hypoglycemia type as covariates.
 Nocturnal 		
 Non-nocturnal 		
Potential persistent-	Safety analysis period (see	The number of participants with at least one
recurrent hypoglycemia	definition in Section 4.6)	event will be summarized and compared by
events:		Fisher's exact test. The number of events will
• identified by		also be provided.
investigators		
 identified by a 		Listings of the events will also be provided.
pre-specified		
criteria		

Abbreviations: HbA1c = hemoglobin A1c; Level 2/3 = Level 2 and Level 3 composite.

Notes: The yearly hypoglycemia rate during defined period is calculated by the number of hypoglycemia within the period/number of days patient at risk within the period*365.25. For rare events, 100 year rate will be provided. The hypoglycemia incidence during defined period indicates if the patient has at least 1 hypoglycemia events within the period (Yes/No).

Group comparisons for hypoglycemia incidence and rate at baseline, baseline HbA1c is not included in the model.

The hypoglycemia rate during the defined period is calculated by the number of hypoglycemia events within the period/number of days a participant is at risk within the period. The hypoglycemia incidence during the defined period indicates if the participant has at least 1 hypoglycemia event within the period (yes/no).

A sensitivity analysis will be performed for selected hypoglycemic endpoints using an alternative definition of continuation of hypoglycemic events. Hypoglycemic events will be considered one hypoglycemic episode until a succeeding glucose value is \geq 70 mg/dL. All such events will be combined into a single episode with the same attributes as defined earlier in this section.

4.6.3.1.2. Hypoglycemic Events Derived from CGM

Level 2, Level 2 ending with BG value \geq 70 mg/dL, and Level 1 or Level 2 hypoglycemic events collected from the sponsor provided CGM are defined in Section 6.6.2. Missing data will be handled as described in Appendix 6 (Section 6.6). The analysis for incidence, event rate, and duration are described in the table below:

Endpoint	Analysis Period	Statistical Method
Event rate of hypoglycemia	Baseline, 0-4, 8-	Negative binomial regression with treatment, baseline
events (24-hour Period) in	12, 22-26, 48-52,	HbA1c and baseline event rate of the corresponding level
events/participant/year:	74-78 weeks,	of hypoglycemia as covariates, log (exposure/365.25 days)
• Level 1 or Level 2	follow-up period	as the offset in the model.
• Level 2		
• Level 2 hypoglycemic		
events ending with BG		
\geq 70 mg/dL		

Endpoint	Analysis Period	Statistical Method
 Incidence of hypoglycemia events (24-hour Period): Level 1 or Level 2 Level 2 Level 2 hypoglycemic events ending with BG ≥70 mg/dL 	Baseline, 0-4, 8- 12, 22-26, 48-52, 74-78 weeks, follow-up period	Logistic regression with treatment, baseline HbA1c and baseline incidence of the corresponding level of hypoglycemia as covariates.
 Duration of hypoglycemic events (24-hour Period) in minutes: Level 1 or Level 2 Level 2 Level 2 hypoglycemic events ending with BG ≥70 mg/dL 	Baseline, 0-4, 8- 12, 22-26, 48-52, 74-78 weeks, follow-up period	For individual CGM sessions (0-4, 8-12, 22-26, 48-52, 74-78 weeks): MMRM model with treatment, strata (country, baseline HbA1c stratum and the type of basal insulin at randomization), session and treatment-by- session interaction as fixed effects, and baseline duration of the corresponding level of hypoglycemic events as a covariate. For Baseline and Follow-up period: ANOVA models only include treatment as covariate.

Abbreviations: ANOVA = Analysis of covariance; CGM = Continuous Glucose monitor; HbA1c = glycated hemoglobin; MMRM = mixed model for repeated measures.

Note: The hypoglycemic rate during defined period is a yearly rate and calculated by number of hypoglycemic events within the period/number of days participant at risk within the period*365.25. The hypoglycemia incidence during defined period indicates if the patient has at least 1 hypoglycemic event within the period (Yes/No).

The total number of episodes, number of episodes that includes Level 2 hypoglycemia episodes, and number of episodes that include glucose readings <54 mg/dL (3.0 mmol/L) but no reported Level 2 hypoglycemia episodes will be summarized for each CGM session.

A listing will be provided for participants with Level 2 hypoglycemia episodes lasting more than 360 minutes.

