Abbreviation: AE = adverse event; ANCOVA = analysis of covariance; CGM = continuous glucose monitoring; CRF = case report form; EAS1 = efficacy analysis set 1; EAS2 = efficacy analysis set 2; HbA1c = hemoglobin A1c; MMRM = mixed model repeated measurement; PSAP = program safety analysis plan; SMBG = selfmonitored blood glucose; TEAE = treatment-emergent adverse event.

All analyses will be implemented using SAS Enterprise Guide Version 7.1 or above.

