6.6. Appendix 6: Derivation of CGM Variables

Blinded CGM will be worn by participants at the following designated weeks:

- Two weeks in screening/lead-in period with the data download at Week 0 (Visit 3),
- Four weeks after the initiation of study treatment with the data download at Week 4 (Visit 7),
- Four weeks near the end of weekly titration period with the data download at Week 12 (Visit 15),
- Four weeks near the primary endpoint with the data download at Week 26 (Visit 22),
- Four weeks near the end of 1-year treatment with the data download at Week 52 (Visit 30),
- Four weeks near the end of study treatment period with the data download at Week 78 (Visit 37), and
- Four weeks after the end of study treatment period with the data download at Week 83 (Visit 802).

Linear interpolation will be used to impute the missing glucose readings during intervals >7 minutes and ≤ 15 minutes. Missing data will be imputed at a 5-minute interval using the BG value before and the one after the interval.

For example, the BG reading before the interval is 50 mg/dL at time 100 min, and the BG reading after interval is 70 at time 115 min, then the missing records will be imputed as:

- at time 105 min, BG reading=50+5*(70-50)/(115-100)=56.7, and
- at time 110 min, BG reading=50+10*(70-50)/(115-100)=63.3.

Glucose reading intervals >15 minutes will be treated as missing data and not be counted in the length of the analysis periods.

As shown in the table below, all the CGM derivations are based on the data from valid CGM periods of a day and period unless otherwise specified.

Period	Definition	Minimum Valid CGM Time Period for a Session		
Valid CGM Day	\geq 70% of expected values	\geq 3 valid CGM days within a visit defines a valid		
(00:00-23:59)	available (≥202 of 288 values)	CGM visit. A valid CGM session only includes valid		
		CGM visits.		
Valid CGM Nighttime	\geq 70% of expected values	\geq 3 valid CGM Nighttime periods within a visit		
(00:00-05:59)	available (≥50 of 72 values)	defines a valid CGM visit. A valid CGM session for		
		nighttime only includes valid CGM visits.		
Valid CGM Daytime	\geq 70% of expected values	\geq 3 valid CGM Daytime periods within a visit defines		
(06:00-23:59)	available 151 of 216 values)	a valid CGM visit. A valid CGM session for daytime		
		only includes valid CGM visits.		

Abbreviation: CGM = continuous glucose monitoring.

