6.6.2. Hypoglycemic Episode

According to the International Consensus Statement (Battelino et al. 2023), the CGM-determined hypoglycemic episodes for Level 1 or 2 and Level 2 are defined as below:

Hypoglycemia Level	Stating Time	Ending Time	Duration
Level 1 or 2 hypoglycemia	Time of the 1st BG of	Time of the last BG of the	Time of the last
(BG <70 mg/dL	BGs <70 mg/dL for	BGs \geq 70 mg/dL for	BG <70 mg/dL – time of
[3.9 mmol/L])	≥15 consecutive minutes	\geq 15 consecutive minutes	the 1st BG <70 mg/dL
Level 2 hypoglycemia (BG <54 mg/dL [3.0 mmol/L])	Time of the 1st BG of BGs <54 mg/dL for ≥15 consecutive minutes	Time of the last BG of the BGs \geq 54 mg/dL for \geq 15 consecutive minutes	Time of the last BG <54 mg/dL – time of the 1st BG <54 mg/dL
Level 2 hypoglycemia	Time of the 1st BG of	Time of the last BG that	Time of the last
ending with	BGs <54 mg/dL for	ensures the BGs ≥70 mg/dL	BG <70 mg/dL – time of
BG ≥70 mg/dL	≥15 consecutive minutes	for 15 consecutive minutes	the 1st BG <54 mg/dL

Abbreviation: BG = blood glucose (as captured in continuous glucose monitor [CGM]).

Note: Starting time and ending time are regardless of number of BG readings.

If the truncated time interval is >7 and \leq 15 minutes, linear interpolation will be used to impute the missing data at 5-minute intervals as described in Section 6.6.

If the truncated time interval is >15 minutes:

- at any time, which make the starting time undeterminable, then do not count this time interval and no episodes start.
- If it is after an episode started, which makes the ending time undeterminable, then the episode ends at the starting time of the truncation.
- If an episode started and continued until the end of a CGM session, then the episode ends at the end of CGM session.

The average duration, incidence, event rate of the Level 1 or 2 and Level 2 hypoglycemia episodes will be analyzed for each CGM session as planned in Section 4.6.3.1.2. The average duration will be calculated by dividing the sum of the duration of individual episodes during the given CGM session by the number of episodes and used in the analysis. The hypoglycemia event rate (events/participant/year) will be calculated by dividing the number episodes by the number of valid CGM days \times 365.25 days.

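### The MMRM for CGM hypoglycemic episode duration adjusts for a baseline duration that is undefined (0/0) when there was no baseline episode, and no rule covers that case

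*SAP*

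**What the plan says.** The Duration row of the table in SAP 4.6.3.1.2 covers three definitions: Level 1 or Level 2, Level 2, and Level 2 ending at 70 mg/dL or above. For the five on-treatment CGM sessions it specifies an MMRM with treatment, the stratification factors, session, treatment-by-session interaction, and "baseline duration of the corresponding level of hypoglycemic events as a covariate". Baseline and follow-up durations are compared by a model with treatment alone.

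SAP 6.6.2 defines the analysed value. Average duration is "calculated by dividing the sum of the duration of individual episodes during the given CGM session by the number of episodes".

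For missing data, 4.6.3.1.2 points to Appendix 6. That appendix deals with sensor gaps ("Glucose reading intervals >15 minutes will be treated as missing data and not be counted in the length of the analysis periods"), with what makes a day or visit valid, and, in 6.6.2, with episodes cut off by a gap or by the end of a session. It does not mention a session with no episodes. It also gives the session lengths: two weeks in the lead-in and four weeks for each on-treatment session.

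The event-rate and incidence rows of the same table adjust for baseline event rate and baseline incidence of the corresponding level.

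**The concern.** A baseline rate of zero and a baseline incidence of no are legitimate values. A mean duration over zero episodes is not a value at all. The duration row is therefore the only one of the three whose baseline covariate disappears when the participant had a clean baseline, and the short baseline window makes a clean baseline likely.

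A mixed model omits any record with a missing covariate. The baseline covariate is the same for all of a participant's records, so one episode-free lead-in removes all five on-treatment sessions, including any with long episodes on study insulin. The protocol gives LY3209590 a half-life of about 17 days, so how long a low lasts is a fair safety question. The planned model would answer it only in participants who were already having lows on their previous insulin, and the SAP does not say that the comparison is restricted in this way.

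The outcome has the same property. On-treatment duration does not exist in a session without an episode, so the comparison is also conditional on something that happens after randomization.

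**Working it through.** The SAP gives no sample size or power for this endpoint, so there is no figure to reproduce. The check is to trace the definition through the model and then size the loss under stated assumptions.

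**Step 1: is there a rule elsewhere?** Baseline multiple imputation appears in SAP 4.1, 4.4.1.2 and 4.4.2.1. In each place it is written for treatment regimen analyses, and it is not invoked for this safety MMRM. A duration that never existed is also not a value missing at random. SAP 4.4.2.1 does describe the inclusion rule for its own MMRMs: a baseline and at least one post-baseline observation. Read across by analogy, that would confirm the loss rather than prevent it.

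**Step 2: inputs for the size.**
- Baseline window 14 days, treatment session 28 days (SAP Appendix 6).
- CGM Level 2 episode rate λ: not in the documents. Assumed 2 to 20 per participant-year.
- Dispersion k: either 0 (Poisson) or the value implied by the only event-rate assumption in the documents, in SAP section 5. For insulin degludec, mean 1.1 and SD 2.6 per year give k = (2.6² − 1.1)/1.1² = 5.66/1.21 = 4.68. These are participant-reported nocturnal events, so this is a stand-in.

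**Step 3: formulas.** With a shared participant frailty, P0(d) = (1 + kλd/365.25)^(−1/k), or exp(−λd/365.25) for Poisson. Among participants with at least one episode in a 28-day session, the share with none at baseline is [P0(14) − P0(42)] / [1 − P0(28)].

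**Step 4: results.**

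| λ per year | k | P0(14) | P0(28) | P0(42) | Share lost |
|---|---|---|---|---|---|
| 2 | 0 | 0.926 | 0.858 | 0.795 | 93% |
| 2 | 4.68 | 0.937 | 0.891 | 0.855 | 74% |
| 20 | 0 | 0.465 | 0.216 | 0.100 | 46% |
| 20 | 4.68 | 0.722 | 0.638 | 0.590 | 36% |

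At 10 per year and k = 4.68 the share lost is 47%, leaving about 139 of 939 participants in that session's comparison.

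**Step 5: sensitivity.** The same sentence in SAP section 5 implies k = (2.6² − 0.67)/0.67² = 13.6 for LY3209590. With that value the share lost runs from 60% at 2 per year to 30% at 20 per year. At 50 per year with k = 4.68 it is 26%.

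**Step 6: Level 1 or Level 2.** Any run of readings below 54 mg/dL is also below 70 mg/dL, so an empty baseline cannot be more likely for this broader definition. For a given k, the share lost falls as the chance of an empty baseline falls, so it is no larger than for Level 2.

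**The case against.** The strongest reply is that the SAP is silent and does not order an exclusion. A programmer could code the missing baseline as zero and keep everyone. That is true, but a zero in that column would mean episodes of no length, and the treatment estimate would then answer a different question. That choice also needs to be written down.

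The second reply is that little rests on this row. Mean episode duration is not in the objectives table, carries no multiplicity control and supports no hypothesis. This stands, and it keeps the point modest.

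Third, the sizes rest on assumed rates and a borrowed dispersion. That also stands: the percentages are illustrations. The undefined covariate does not depend on them.

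Two stronger readings are tempting, and the documents support neither.
- A reader might infer that the plan removes new-onset hypoglycemia from the safety assessment. It does not. The same participants stay in the CGM rate and incidence models, in time below 54 mg/dL before Weeks 26, 52 and 78 (a listed secondary safety endpoint), in the minutes-per-day variables of SAP 6.6.1, in the follow-up-period duration comparison, and in the listing of Level 2 episodes over 360 minutes, which needs no baseline value.
- A reader might infer that the exclusion biases the comparison between arms. Baseline duration is fixed before randomization, so excluding on it restricts both arms alike. Conditioning on an on-treatment episode is a separate matter, and it calls for a label on the result.

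**Conclusion.** The point holds within a narrow scope. Following the formula in SAP 6.6.2 and the model in 4.6.3.1.2 as written, participants with no baseline episode of the given level have an undefined covariate, and standard MMRM handling drops all their on-treatment sessions from the duration comparison. The consequence is lost precision and a result that describes only participants already having episodes on their previous insulin.

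The loss is about 36% to 93% of participants with an on-treatment Level 2 episode, assuming 2 to 20 episodes per participant-year, dispersion between 0 and 4.68, a constant rate and a shared frailty. A higher rate or dispersion would lower it. The conclusion also assumes that 0/0 is left missing.

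This goes beyond missing detail, because the two neighbouring rows already use covariates that are defined at zero episodes. It should be corrected, but it does not touch the primary or key secondary analyses.

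**What to change.** In the Duration row of SAP 4.6.3.1.2, replace baseline duration with baseline percentage of time below the same threshold: below 54 mg/dL for both Level 2 definitions, and below 70 mg/dL for Level 1 or Level 2. SAP 6.6.1 already derives both, and they are defined, including at zero, for everyone with a valid baseline session.

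Add a sentence saying that a session without an episode contributes no duration. Label the result as conditional on having an on-treatment episode, and state that it is to be read alongside the planned time-below-range analyses, where a session with no time below the threshold counts as zero.

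The cost is SAP wording and one changed covariate, with no new data or derivation. The downside is a slightly weaker covariate for participants who do have baseline episodes.
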